### **2.4 Exploratory Phase II objectives (Crossover Treatment)**

**2.4.1** To evaluate secondary endpoints within patients crossing over to dual agent nivolumab plus ipilimumab after experiencing progressive disease while receiving single agent nivolumab.

**2.4.2** To evaluate correlative science objectives endpoints within patients crossing over to dual agent nivolumab plus ipilimumab after experiencing progressive disease while receiving single agent nivolumab.

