- C Every 6 weeks for 12 weeks, then every 8 weeks until evidence of progression or relapse. Scans may be performed +/- 7 days from scheduled date. During the first 12 weeks of therapy, patients can be considered for continuation of treatment (see [Section 7.1](#) for further details and footnote D below). Confirmatory scans to be obtained at least 4 weeks following documentation of objective response (see [Section 11.0](#)). Response assessment should include assessment of all sites of disease and use the same imaging method as was used at baseline. For patients receiving initial treatment beyond 2 years from randomization date; scans may be performed every 3 months for year 3, every 4 months for year 4, every 6 months for year 5 and then yearly thereafter. One confirmatory scan continues to be required if patient achieves a response for the first time and during this period. Thereafter, returning to the assessment schedule.
- D If there is evidence of progression in the first 12 weeks, treatment is allowed to be continued. The patient's baseline assessment is now the 1st assessment showing progression (not the pre-study disease assessment) and is used for the remainder of the patient's initial treatment assignment (not crossover). Contact the Data Manager or Study Chair for questions. If this occurs, an additional scan is to be scheduled 4 weeks from the regular scan (i.e. at week 10 or 16). Thereafter, the patient will have a scan every 8 weeks. See also [section 7.1](#) for further information.
- E. **Crossover Patients Only:** For patients who crossover to dual agent therapy, a baseline scan is required  $< 28$  days prior to re-registration. After initiation of dual agent therapy scans are every 6 weeks for 12 weeks, then every 8 weeks until evidence of progression or relapse (scans may be done +/- 7 days from due date). During the first 12 weeks of therapy, patients can be considered for continuation of treatment (see [Section 7.1](#) for further details and footnote D above with the appropriate reset for baseline disease measurement. Contact the Data Manager or Study Chair for questions). Confirmatory scans are to be obtained at least 4 weeks following documentation of objective response (see [Section 11.0](#)). Response assessment should include assessment of all sites of disease and use the same imaging method as was used at the baseline measurements associated with crossover. For patients receiving crossover

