## 7.2 Crossover to Dual Agent Nivolumab and Ipilimumab upon Progression on Arm 1 (single agent nivolumab)

Upon documentation of progression on arm 1 and confirmation of eligibility criteria as per [Section 3.4](#), patients may be re-registered and initiate dual-agent therapy. All parameters outlined in [section 7.0](#) are applicable. NOTE: Treatment beyond progression in the first 12 weeks, as per [section 7.1](#), is applicable to patients receiving crossover dual agent therapy.

Administer nivolumab prior to ipilimumab (follow institutional standard for timing between agents) as specified below:

Agent	Dose & Route	Frequency	Cycle Length (ReRx)
nivolumab	3mg/kg IV over 30 minutes	Every 3 weeks	42 days
ipilimumab	1mg/kg IV over 90 minutes	Every 3 weeks	42 days

\*\*The above regimen will be followed for 4 doses, followed by:

Agent	Dose & Route	Frequency	Cycle Length (ReRx)
nivolumab	3mg/kg IV over 30 minutes	Every 2 weeks	42 days

Though treatment is every 2 or 3 weeks, **a cycle will consist of 6 weeks in length** and therapy can be continued until patient develops progressive disease or unacceptable toxicity or withdraws from treatment. In the absence of these 3 events, treatment will continue for a maximum of 108 weeks (i.e. 18 cycles) including the single agent nivolumab received prior to crossover to dual agent therapy.

To determine response via RECIST v1.1, patients will undergo radiographic imaging every 8 weeks while on study treatment.

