### 11.1 Schedule of Evaluations:

**Initial Treatment (Assigned at Registration/Randomization):** For the purposes of this study, patients should be evaluated every 6 weeks for 12 weeks, and then every 8 weeks thereafter. In addition to a baseline scan, confirmatory scans should also be obtained 4 weeks following initial documentation of objective response. See [Section 7.0](#) for further details. Additionally, see [Section 7.1](#) for instructions for how to treat, rescan, and use the proper disease assessment (e.g. baseline, reset baseline, or crossover baseline) for comparison in patients who demonstrate progressive disease within the first 12 weeks of study participation. For patients receiving initial treatment beyond 2 years from randomization date; scans may be performed every 3 months for year 3, every 4 months for year 4, every 6 months for year 5 and then yearly thereafter. One confirmatory scan continues to be required if patient achieves a response for the first time and during this period. Thereafter, returning to the assessment schedule.

**Crossover Treatment:** Patients having crossed over to dual agent therapy following progression of disease while receiving single agent nivolumab (per [section 3.4](#)) should be evaluated every 6 weeks for 12 weeks, and then every 8 weeks thereafter. As per [section 5.0](#), patients must have imaging performed within 28 days of re-registration to dual agent therapy. This scan will be the baseline scan for patients to determine response to dual agent therapy. For patients receiving crossover treatment beyond 2 years from date of crossover, scans may be performed every 3 months for year 3, every 4 months for year 4, every 6 months for year 5 and then yearly thereafter. One confirmatory scan continues to be required if patient achieves a response for the first time and during this period. One confirmatory scan continues to be required if patient achieves a response for the first time and during this period. Thereafter, returning to the assessment schedule.

See [Section 7.0](#) for further details. Additionally, see [Section 7.1](#) for instructions for how to treat, rescan, and use the proper disease assessment for comparison for patients who demonstrate progressive disease within the first 12 weeks of study participation.

In all cases, supporting documentation of response and progression should be submitted, per [Section 6.1.1](#).

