## 13.4 Secondary Endpoints

- Evaluating adverse event rates (NCI CTCAE v4.0), within each study treatment arm. Categorical data analysis will be used to summarize adverse event rates and as a maximum severity during treatment for each patient and AE classification.
- Evaluating duration of response, clinical benefit rate (CBR), progression-free survival (PFS), and overall survival (OS), within each study treatment arm. Patients having PD within the first 12 weeks of starting treatment which is not a PD at their 4 week confirmation assessment will not be classified as having PD for time to event analyses. That is, estimates for response, CBR, and PD endpoints will not be censored at the first PD in such cases. Patients who are unable to continue treatment for a 4-week confirmation of PD occurring within the first 12 weeks of treatment will be counted as having PD at their first date of PD during the treatment period (eg, initial, crossover). In addition, disease assessment data beyond the date of crossover will not be included in the evaluation of the primary endpoint and for those patients crossing to dual agent treatment from single agent treatment. Such patients will be censored for estimating

duration of response, CBR, and PFS. Patients will be additionally censored at their most recent disease assessment prior to receiving any anti-cancer therapy after ending study treatment.

Kaplan-Meier methodology will be used to evaluate time to event endpoints: duration of response (time from first response to disease progression), PFS (time from randomization to the earliest of either disease progression or death from any cause), and OS (time from randomization to death from any cause). The CBR will be evaluated by counting up the number of patients with a response or stable disease (PR, CR, SD) and dividing by the total number of evaluable patients. Cumulative Incidence Function methodology may be used, as appropriate.

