- Confirmed response and secondary endpoints will be evaluated in patients who crossover from single agent nivolumab to dual agent treatment following progression. The date used for the calculations of duration of response, TTP, PFS, and OS will be the date the patient initiated crossover treatment with dual agent therapy.

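### As literally written, Section 13.5 dates crossover duration of response from the start of crossover treatment instead of first response, which adds each responder's time to response to the result

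*Combined protocol and SAP*

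**What the plan says.** Objective 2.4.1 is exploratory: "To evaluate secondary endpoints within patients crossing over to dual agent nivolumab plus ipilimumab" after progression on single-agent nivolumab. Section 2.2.2 lists duration of response among those secondary endpoints.

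Section 13.4 defines the time-to-event endpoints for the initial treatment period. It gives "duration of response (time from first response to disease progression" and "PFS (time from randomization to the earliest of either disease progression or death from any cause", and it also counts overall survival from randomization.

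For crossover patients Section 13.5 sets one date rule for four endpoints together: "The date used for the calculations of duration of response, TTP, PFS, and OS will be the date the patient initiated crossover treatment".

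On imaging, Section 11.1 requires a scan within 28 days of re-registration and says: "This scan will be the baseline scan for patients to determine response to dual agent therapy". Footnote E of the Section 5.0 calendar says: "After initiation of dual agent therapy scans are every 6 weeks for 12 weeks, then every 8 weeks until evidence of progression or relapse", with the allowance that "scans may be done +/- 7 days from due date". Section 7.2, the crossover treatment section, says instead that "patients will undergo radiographic imaging every 8 weeks while on study treatment".

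**The concern.** Replacing randomization with the crossover start makes sense for PFS and OS, because randomization precedes a treatment period that is no longer of interest. Duration of response never started at randomization. Its origin is an event on treatment, and a duration cannot begin before the response exists. By naming it in the same list, Section 13.5 swaps first response for the first day of crossover treatment.

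The consequence is an endpoint that keeps its name but measures something else. It includes the interval before response, during which a responder is by construction free of progression. A Kaplan-Meier curve on that scale therefore starts with event-free time that owes nothing to how long responses last. Section 13.5 says the exploratory and correlative analyses should help in designing larger phase III studies, so someone may plan from this figure. Section 11.5 sends readers to the Statistical Considerations for formal variable definitions, and the only crossover date rule there is the sentence in 13.5. A programmer who follows it to the letter computes the longer interval.

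**Working it through.** The plan gives no estimate, sample size or power that depends on the crossover origin, so there is no figure to reproduce. The check is an identity, followed by its size on the protocol's scan schedules.

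**Inputs**
- Origin under 13.4: first response. End: progression.
- Origin under 13.5 for crossover patients: start of crossover treatment.
- Response is judged against a new pre-crossover baseline scan (11.1), so it can be recorded only after crossover treatment starts.
- Scheduled scans under footnote E of Section 5.0: weeks 6 and 12 from the start of dual therapy, then every 8 weeks (next at week 20), each within 7 days either way. The first scan therefore falls at weeks 5 to 7.
- Scheduled scans under Section 7.2: every 8 weeks, so the first is at week 8.

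**Identity.** For any responder, with the same end date (progression or censoring):

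(end − crossover start) − (end − first response) = first response − crossover start = time to response.

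The difference is positive for every responder, progressed or censored.

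**Size.** Months = weeks × 7 / 30.4375. For week 6: 42 / 30.4375 = 1.38. The documents give no true duration of response, so 3, 6 and 12 months are assumptions used only to show proportion. Each cell is the assumed duration plus the time added, with the percentage excess.

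| First response seen at | Months added | True 3 months | True 6 months | True 12 months |
|---|---|---|---|---|
| Week 5 | 1.15 | 4.15 (+38%) | 7.15 (+19%) | 13.15 (+10%) |
| Week 6 | 1.38 | 4.38 (+46%) | 7.38 (+23%) | 13.38 (+11%) |
| Week 7 | 1.61 | 4.61 (+54%) | 7.61 (+27%) | 13.61 (+13%) |
| Week 8 (Section 7.2) | 1.84 | 4.84 (+61%) | 7.84 (+31%) | 13.84 (+15%) |
| Week 12 | 2.76 | 5.76 (+92%) | 8.76 (+46%) | 14.76 (+23%) |
| Week 20 | 4.60 | 7.60 (+153%) | 10.60 (+77%) | 16.60 (+38%) |

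**Relation to PFS.** Under 13.5 crossover PFS also starts at crossover start. For a responder who progresses, or who is censored alive, the two intervals then have the same start and end and are equal. They differ for a responder who dies without progression, because 13.4 ends PFS at progression or death but ends duration of response at progression only.

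**The case against.** The best defence is that the sentence is loosely drafted and does not redefine the endpoint. It speaks of the date used in the calculations, not of a start date. The sentence before it carries the secondary endpoints over to crossover patients, and 13.4 already defines those. The authors may have wanted only to replace randomization as the reference date, much as 11.1 sets a new baseline scan. That intention is plausible, which is why the point is put as what the text literally says. It does not remove the problem: duration of response is named in the list, and nothing elsewhere restores first response as its origin for crossover patients.

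The second defence concerns consequence, and it stands. Section 13.1 calls the crossover analyses exploratory and promises careful handling of the data, and 13.5 rules out direct comparison of the single and dual regimens. Section 13.3 keeps post-crossover data out of the primary endpoint, and the criteria for promising activity in 13.3.1 to 13.3.3 rest on confirmed response.

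A reader might infer two stronger things.
- One is that the rule biases a comparison in favour of adding ipilimumab after progression. The documents plan no such comparison, and crossover patients are selected by progression on nivolumab, so the initial arms are not their controls.
- The other is that the crossover endpoint adds nothing to PFS. That goes too far: PFS also counts deaths and is summarised in all crossover patients, while duration of response is summarised in responders.

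The size also has limits. An unscheduled early scan could record a response before week 5, so 1.15 months is not a strict minimum. The percentages depend wholly on the assumed durations.

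**Conclusion.** The point holds as a conflict between two stated definitions. Followed to the letter, 13.5 overstates each crossover responder's duration, relative to the 13.4 definition, by exactly the time to response. For a response first seen at the first scheduled scan, that is 1.15 to 1.61 months on the footnote E schedule or 1.84 months at week 8 under Section 7.2. It is 2.76 months at week 12 and 4.60 months at week 20. The direction and the identity need no assumption beyond the literal reading. The months assume that responses are picked up at scheduled scans.

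The reach is narrow: one exploratory endpoint in the crossover group. Within that reach the figure reported under objective 2.4.1 would be wrong, and it could not be read as the same quantity as duration of response in the initial arms. A correction is worth making before the crossover analysis is programmed.

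**What to change.** Replace the date sentence in 13.5 with wording such as: *For crossover patients, TTP, PFS and OS are calculated from the date crossover treatment was initiated. Duration of response is calculated from the date of first documented response on crossover treatment, judged against the crossover baseline set in Section 11.1, to disease progression, as in Section 13.4.*

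Separately, reconcile the crossover imaging intervals in footnote E of Section 5.0 and in Section 11.1 with the one in Section 7.2, since the time to a recorded response depends on them.

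The cost is one sentence. Sections 6.1.1 and 11.1 already require documentation of response and progression, so no new data, scans or patients are needed. Reported crossover durations will be shorter than under the literal rule.

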### 13.6 Total Sample Size, Accrual Duration, and Anticipated time to study completion

Although, we observed an unprecedented accrual rate for the initial portion of this study and pre-registered over 80 cases within 9-10 weeks (August-October 2015) and 15-17 cases within

5 hours (March 2016) and there is continued interest in this trial, we conservatively estimate that we can enroll a maximum of 2 patients per month within each of the histologic cohorts.

- If both GIST arms terminate at the interim analysis, we will need a maximum of 76 patients across 6 arms and will enroll these cases in 13 months.
- If at both GIST arms complete full enrollment, we will need a maximum of 110 patients. These cases will be enrolled in 24 months, without a suspension.

Therefore, we plan to enroll a minimum of 76 patients to a maximum of 110 patients across all 6 cohorts and arms (per Update #06), which includes 10% over accrual for non-evaluable patients. We will pre-register a maximum of 82 and 120 cases to obtain these enrollment figures and based on current screen failure rates at the time of central pathology review. The number of pre-registrations and registrations/randomizations to each group are summarized below:

**New Pre-registration & Enrollment, by Group (Per Update #06)  
(Two (2) Arms in 1 Group)**

Group	Step 1 a	Step 2 a	Group Total
LPS	28 (30) b	N/A	28 (30)
UPS/MFH	28 (30)	N/A	28 (30)
GIST	20 (22)	34 (38)	54 (60)
Step Total	76 (82)	34 (38)	110 (120)

a) Total for both arms.

b) Registered (Pre-registered)

Assuming that patients were allowed to remain in treatment for a maximum of 2 years and that we would need 6 months for quality assurance for the interim and final analyses, we estimate the maximum duration of the study to be an additional 36 months (3 years) from activation of Update #06.

Inclusive of those patients pre-registered and enrolled prior to Update #06 and for administrative purposes, this trial is targeting a maximum of 216 (i.e., 96 + 120) patients to be pre-registered and a maximum of 195 (i.e., 85 + 110) patients to complete final registration/randomization onto the study.

### 13.7 AE Stopping Rule

The stopping rule specified below is based on the knowledge available at study development. We note that the Adverse Event Stopping Rule may be adjusted in the event of either (1) the study re-opening to accrual after any temporary suspension or (2) at any time during the conduct of the trial and in consideration of newly acquired information regarding the adverse event profile of the treatment(s) under investigation. The study team may also choose to suspend accrual because of unexpected adverse event profiles that have not crossed the specified rule below.

Accrual will be temporarily suspended to this study if at any time we observe events considered at least possibly related to study treatment (i.e., an adverse event with attribute specified as

"possible", "probable", or "definite") that satisfy any of the following criteria for each arm separately and applies to the treatment patients were initially randomized to:

- If at any time, 4 of the initial 10 treated patients or 40% or more of all patients (i.e. when accrual is greater than 10 patients) have experienced a  $\geq$  grade 3 adverse event.
- If at any time, 2 patients have experienced a grade 5 adverse event (non -progressive disease).
- In addition, each grade 5 event will be reviewed on a case by case basis in a real time fashion to determine whether study accrual should be suspended. We may suspend accrual after just 1 grade 5 AE, if needed.
- In addition, for patients who are assigned to single agent nivolumab and cross over to dual agent therapy, the same 3 conditions would trigger a temporarily suspension and would not allow further patients to re-register and receive dual agent therapy.

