### ARM 2\*\*

Administer nivolumab prior to ipilimumab (follow institutional standard for timing between agents) as specified below:

Agent	Dose & Route	Frequency	Cycle Length (ReRx)
nivolumab	3mg/kg IV over 30 minutes	Every 3 weeks	42 days
ipilimumab	1mg/kg IV over 90 minutes	Every 3 weeks	42 days

\*\*The above regimen will be followed for 4 doses, followed by:

Agent	Dose & Route	Frequency	Cycle Length (ReRx)
nivolumab	3mg/kg IV over 30 minutes	Every 2 weeks	42 days

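### Section 13.7 counts related deaths on the dual-agent regimen separately for Arm 2 and for crossover patients, so one death by each route brings mandatory review but not the automatic two-death suspension

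*Combined protocol and SAP*

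**What the plan says.** Section 13.7 (AE Stopping Rule) covers events at least possibly related to treatment. Its criteria are applied "for each arm separately and applies to the treatment patients were initially randomized to". The fatal-event criterion reads "If at any time, 2 patients have experienced a grade 5 adverse event", with progressive disease excluded. A second automatic criterion is met when 4 of the first 10 treated patients, or later 40% or more, have a related event of grade 3 or higher.

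Below these thresholds the section adds review and discretion:

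- "each grade 5 event will be reviewed on a case by case basis in a real time fashion"
- "We may suspend accrual after just 1 grade 5 AE, if needed"
- "The study team may also choose to suspend accrual because of unexpected adverse event profiles that have not crossed the specified rule below"

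A last bullet covers Arm 1 patients who cross over. For them, "the same 3 conditions would trigger a temporarily suspension and would not allow further patients to re-register and receive dual agent therapy". No sentence in 13.7 combines Arm 2 with crossover patients.

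The treatment is the same by either route. Section 7.0 gives Arm 2 nivolumab 3 mg/kg and then ipilimumab 1 mg/kg every 3 weeks, and continues "The above regimen will be followed for 4 doses, followed by" nivolumab every 2 weeks. Section 7.2 gives crossover patients the same agents, doses, order and schedule, introduced by "Administer nivolumab prior to ipilimumab (follow institutional standard for timing between agents) as specified below". Section 4.6 describes crossover as a move to Arm 2.

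**The concern.** The sponsor chose two related deaths as the point at which suspension stops being a matter of judgment. As written, whether that point is reached for the dual-agent regimen depends on how each patient came to the regimen, not only on how many died on it. Fatal immune toxicity is foreseeable: the cardiac table in Section 8.2.2 notes deaths from myocarditis, and the ipilimumab risk list in Section 9.4.2 warns of fatal immune-mediated events.

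The stated consequences also differ by route. An Arm 2 trigger suspends study accrual, whereas a crossover trigger stops re-registration. A death by one route therefore adds nothing to the automatic protection of patients entering by the other.

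**Working it through.** **Applying the rule.** Section 13.7 gives no operating characteristics, so there is no figure of the plan's own to reproduce. Take one related death in Arm 2 and one after crossover.

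- Arm 2 count: 1, below 2.
- Crossover count: 1, below 2.
- If the crossover death is also charged to the arm of randomization, it goes to Arm 1, and Arm 2 still stands at 1.
- Combined dual-agent count: 2, which would trigger.

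**Size: inputs.** From the documents, Arm 2 could be 86 (38 + 12 + 12 + 24 evaluable, Sections 13.3.1 to 13.3.3), 42 (about half of the 85 enrolled before Update #06, Section 13.6) or 97 (about half of the 195 maximum, Section 13.6). Two inputs are assumptions: the number of crossovers, n_c (20; range 10 to 40), and the related-death risk, q (1%; range 0.5% to 3%). Counts are taken per treatment across cohorts.

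**Formulas.** Let A ~ Binomial(n_2, q) be related deaths in Arm 2 and C ~ Binomial(n_c, q) those after crossover.

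- Current grade 5 trigger: 1 − P(A ≤ 1) × P(C ≤ 1)
- Increase from adding the combined count: P(A = 1) × P(C = 1)

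**Worked case, n_2 = 86, n_c = 20, q = 1%.** P(A = 0) = 0.421 and P(A = 1) = 0.366, so P(A ≤ 1) = 0.787. P(C = 0) = 0.818 and P(C = 1) = 0.165, so P(C ≤ 1) = 0.983. The current trigger is 1 − 0.787 × 0.983 = 0.226. The increase is 0.366 × 0.165 = 0.060, giving 0.286.

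| Arm 2 | Crossovers | Risk | Current | With combined count | Increase |
|---|---|---|---|---|---|
| 42 | 20 | 1% | 8.2% | 12.8% | 4.6 points |
| 86 | 20 | 1% | 22.6% | 28.6% | 6.0 points |
| 97 | 20 | 1% | 26.6% | 32.7% | 6.1 points |
| 86 | 10 | 0.5% | 7.0% | 8.4% | 1.3 points |
| 86 | 40 | 2% | 60.8% | 72.0% | 11.2 points |

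With 86 in Arm 2, the last two rows are the smallest and largest increases among the values evaluated (10, 20 and 40 crossovers; 0.5%, 1%, 2% and 3%). Keeping Arm 2 at 1% (86 and 20 patients), a crossover risk of 0.5% gives an increase of 3.3 points and a risk of 2% gives 10.0 points.

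**If crossover deaths also count toward Arm 1.** One crossover death plus one other Arm 1 death would then already suspend accrual. The gap remains only when Arm 1 has no other related death, so the increase is multiplied by (1 − q_1)^86, with 86 in Arm 1 and q_1 its assumed risk:

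- q_1 = 0.5%: 0.0605 × 0.650 = 0.039, or 3.9 points.
- q_1 = 1%: 0.0605 × 0.421 = 0.025, or 2.5 points.

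**What these figures leave out.** They concern the grade 5 count alone. Sections 1.5 and 1.6 cite related grade 3–4 rates on the combination of 53% (melanoma) and 43% (renal cell, two dose groups pooled). In simulation with 86 patients, Arm 2 crosses the grade 3-or-higher criterion with probability about 95% if the true rate is 43%, 49% if it is 30%, and 15% if it is 20%.

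**The case against.** The strongest reply is that the plan already deals with this case. Each grade 5 event must be reviewed as it occurs, expressly to decide on suspension, and one death can be enough. The gap matters only if two reviews, the second made with the first death known, both decide against suspending. Section 13.7 also lets the rule be adjusted on new safety information. This stands, and it is why the priority is modest. It does not explain why an automatic threshold that exists alongside that discretion should depend on the route to the regimen.

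Separate counting also has a rationale. Crossover patients have progressed after at least 10 weeks of nivolumab (Section 3.4), and each consequence is matched to its group. That supports keeping the separate counts; it is no argument against adding a combined one.

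Timing limits the benefit as well. The initial cohort closed on 02/02/2017 (Section 4.8), and re-registration requires the last nivolumab dose within 12 months (Section 3.4.2). The figures are whole-trial totals, and a count reached after both routes have closed has nothing left to suspend.

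Three stronger readings are tempting and not supported:

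- *Two deaths could pass without response.* Review of each is mandatory.
- *Automatic suspension is unlikely without the change.* The grade 3-or-higher criterion may suspend accrual independently, and each death also counts as one patient toward it.
- *The gap is far larger if each arm means each cohort's arm.* On that reading, with 86 in Arm 2, the probability goes from 10.5% to 28.6%. But 12.1 of those 18.2 points (10.5% to 22.6%) come from merging the four Arm 2 cohorts; only 6.0 come from crossover. The larger figure does not measure this gap.

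**Conclusion.** The point holds as a limited gap in the automatic rule. One related death in Arm 2 and one after crossover meet neither two-death count, although the regimen is the same, and nothing in the documents combines them. This conclusion rests on the wording alone.

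The size is illustrative. At 1% risk and 20 crossovers, both assumed, the grade 5 trigger becomes about 5 to 6 points more likely. With 86 per arm and Arm 1 risk of 0.5% to 1%, the increase is about 2.5 to 4 points if crossover deaths also count toward Arm 1. The calculation further assumes independent patients, equal risk by both routes except where stated, and that something remains open to suspend. The change is worth making because it is cheap and concerns patient safety, but it is not urgent.

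**What to change.** Keep every existing count and add to Section 13.7: *Related grade 5 events (non-progressive disease) are also counted across all patients receiving dual-agent therapy, whether randomized to Arm 2 or crossed over; the second such event temporarily suspends study accrual and re-registration under Section 4.6, whichever is still open, until reviewed.*

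The section number avoids confusion with the table in Section 13.6, where Step 2 means the second GIST enrollment step. The grade 3-or-higher criterion stays as it is. Because the separate counts remain, a signal confined to one group is not diluted. If the sponsor intends cohort-by-cohort counting within Arm 2, it should say so, because this sentence would then combine cohorts too.

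The cost is one sentence. No new data or committee is needed: Section 9.3 already requires 24-hour reporting of any death within 30 days of the last dose and of later related deaths. The downside is a slightly more likely temporary pause, which would also hold up enrollment to nivolumab alone.
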